#### **10.5** Symptoms During DBPCFC

During each food challenge, the severity of pre-specified symptoms (hives, throat tightness, throat swelling, throat discomfort, hoarseness, laryngeal edema, skin flushing, pruritus, rhinorrhea, sneezing, nasal congestion, cough, wheezing, dyspnea, abnormal pain, abdominal cramping, nausea, vomiting) is rated as none, mild, moderate, severe, or life-threatening at each dose level of each food product. In addition, the presence of dose-limiting symptoms is recorded.

Symptoms at the Screening and Exit DBPCFCs will be listed by subject.

Symptoms will be summarized separately for symptoms during Screening DBPCFC (separately for the Safety and Screening DBPCFC Only populations) and Exit DBPCFC (for the Safety population). Subjects will be counted at most one time per symptom for each summary, at the most severe level recorded for that subject. The maximum dose severity of any symptom, and the presence of any dose limiting symptoms, will also be summarized.

## **10.6** Symptoms During Escalation Dosing

During each escalation dosing, the severity of pre-specified symptoms is similarly rated as none, mild, moderate, severe, or life-threatening. In addition, the presence of dose-limiting symptoms and whether the dose was tolerated is recorded for each escalation dose.

Symptoms will be listed by subject, time point, and dose level. Maximum severity by symptom, maximum overall severity, and presence of any dose limiting symptoms will be summarized across all dose levels. Symptoms, maximum severity of any symptom, presence of dose limiting symptoms, and whether the dose was tolerated will be summarized for each dose level. If a subject is administered the same dose at more than 1 up-dosing visit (either the subject remained at the same dose as the previous visit, or a subject had a prior dose increase and subsequent dose reduction), the most severe symptoms and dose-limiting symptoms will be summarized for that dose level.

#### **10.7** Symptoms During At-Home Dosing

A description of at-home dosing symptoms, and their onset and resolution times, will be collected in the daily diary and listed by subject and date. The number of days with any at-home dosing symptom will be listed by subject and summarized by treatment group.

#### 10.8 Pregnancy Test Results

Pregnancy test results will be listed by subject and visit.

#### **10.9** Spirometry and PEFR

Spirometry (forced expiratory volume, FEV1) and/or Peak Expiratory Flow Rate (PEFR) assessments are performed prior to any DBPCFC. PEFR is also performed at each up-dosing visit. Three attempts of FEV1 are performed, and the best (highest) value flagged in data listings. Similarly, three attempts of PEFR are performed, and the best (highest) value flagged in data listings. Only the best FEV1 value and the best PEFR value will be summarized.

Forced vital capacity (FVC), predicted FVC, predicted FEV1, predicted FEV1/FVC are also listed, and both results and changes from baseline summarized by treatment group and overall for the Safety population. PEFR is listed and summarized similarly.

## 10.10 Vital Signs

BMI will be calculated as (weight in kilograms)/ (height in meters).

Vital signs (pulse rate, systolic/diastolic blood pressure, body temperature, height, BMI, and weight) will be listed by subject and visit. Observed values and change from baseline will be summarized by visit and treatment group.

#### **10.11** Physical Examination

Physical examination results will be listed by subject and visit. Results will be summarized by body system and visit. A shift table of changes from baseline to each post-baseline visit, plus to the worst post-baseline visit, within treatment group and body system will also be provided.

The worst post-baseline result will be defined, within body system, as:

- Abnormal, if any abnormal result is present after the first dose of randomized study treatment
- Normal, if all non-missing results after the first dose of treatment are normal
- Not Done, if no results are present after the first dose of treatment

#### **10.12** Physician Global Assessment

A 100-mm VAS will be used by the investigators to assess overall disease activity as a marker for safety (0 = no disease activity, 100 = very severe disease activity). VAS scores will be listed by subject and date. Observed values and changes from baseline will be summarized by treatment group and visit for the Safety population. Summary statistics will include 95% confidence intervals for point estimates of the mean. The treatment difference in mean changes from baseline with 95% confidence intervals will also be summarized.

# **11 EXPLORATORY ANALYSES**

#### **11.1 Epinephrine Use as Rescue Medication**

Epinephrine use is defined as any rescue medication with a preferred name of 'EPINEPHRINE' when coded as described in Section 10.2, and with documentation of administration to a subject on a specific date.

All subjects, per protocol, are required to have epinephrine autoinjectors for use in case of a suspected anaphylactic reaction occurring outside of the clinic. There are, however, differences in how, and even if, physicians record the prescription of epinephrine autoinjectors for as-needed (PRN) use. As a consequence of this, the presence or absence of a PRN prescription for epinephrine cannot be taken to indicate epinephrine usage, regardless of whether the prescription was written prior to, or after, enrollment in the study. What is important is to be able to quantitate the number of subjects receiving doses of epinephrine and the number of doses. As epinephrine should only be administered to treat a discrete allergic reaction, each dose of epinephrine should be closely temporally associated with a specific safety event. In cases where a PRN epinephrine prescription is issued after the start of study-product dosing, the sites are queried as to if, and when, epinephrine was actually administered and to treat what specific event.

Epinephrine use will be categorized by the following time points, based on epinephrine use on the same day(s) as any of the following events:

- Any use on the same date as an accidental exposure (defined as a recorded food allergy episode) occurring on or after the first dosing date of randomized treatment
- Screening DBPCFC, further categorized into
  - Peanut Challenge: if epinephrine is administered on the day of a peanut challenge, the default assumption will be that the epinephrine administration was in response to a peanut-related event, regardless of whether a placebo challenge was also conducted on the same day)
  - Placebo Challenge
- Post Screening DBPCFC, Prior to Randomized Study Treatment
- Visit 01 (including all days of that visit)
- Up-dosing Visit (including any day in which dose is increased)
- On-Treatment (any day during the active treatment period, excluding Visit 01 and Up-dosing Visits)
- Exit DBPCFC, further categorized into
  - Peanut Challenge (with same provisos as for Screening DBPCFC)
  - Placebo Challenge
- Post Treatment or Post Exit DBPCFC (any day after the Exit DBPCFC, if administered, or the day after the last dosing date of randomized study treatment)

As described in Section 10.3, if a subject undergoes an Up-dosing visit but the dose stays the same or decreases, that day will be classified as On Treatment. If both

peanut and placebo DBPCFCs were on the same date (either at Screening or Exit), any epinephrine use on that date will be categorized as used for the peanut challenge.

Frequency of use will be summarized overall (for any frequency) and by frequency administered (Once, twice, etc.). The number of subjects at risk at each timepoint will be used as the denominators; for instance, only subjects undergoing Exit DBPCFC will be used as the denominator for epinephrine use during Exit DBPCFC. Summaries will be presented separately for the Safety and Screening DBPCFC Only populations.

# **11.2 Summary of Rescue Medications**

Non-study medications used during the course of the study may be recorded on CRF pages other than the Concomitant Medications CRF page. Information about epinephrine and other rescue medications and their frequency of use, will be consolidated and summarized for use in the clinical study report (CSR). A table shell will be finalized prior to database lock but not included in the SAP.

## **11.3 Anaphylaxis Episodes**

All reported anaphylactic reaction episodes will be listed by subject. The number of subjects experiencing such a reaction, the number of reactions per subject, and the total number of reactions reported will be summarized. Episodes will also be summarized by the episode trigger.

These summaries will be repeated for:

- Episodes where epinephrine is administered on the same date (based on the Concomitant Medication CRF pages)
- Episodes where epinephrine is not administered on the same date
- Episodes which occur on the same date as accidental exposure to a food allergen
- Episodes which do not occur on the same date as accidental exposure to a food allergen

These summaries will be produced separately for the Safety and Screening DBPCFC Only populations.

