#### **10.2** Prior and Concomitant Medications and Therapies

All medications recorded on the Concomitant Medications CRF page will be coded using the World Health Organization drug dictionary (WHODRUG), March 2013 version. Medications will be listed and summarized by Anatomical Therapeutic Chemical (ATC) Level 1 and Preferred Name.

Prior medications are defined as those which are only taken prior to the beginning of the active treatment period. Concomitant medications are medications taken at any time during the active treatment period, or those which are able to be taken during that period. Any medications recorded which begin after the last dose of randomized study treatment will also be classified as concomitant medications. As needed (*PRN*) medications, which may not be taken for long periods of time but which are prescribed to the subject, and the prescription period overlaps with the active treatment period, will be considered concomitant medications.

All non-study medications will be listed by subject. Rescue medications and medications prescribed as a result of an anaphylactic reaction will be listed by subject. Further presentation of epinephrine use data is described in Section 11.1.

Concomitant medications will be summarized by treatment group and overall. Subjects will be counted no more than one time per Preferred Name and no more than 1 time per ATC Level 1 in the summary. A similar summary will be presented for concomitant medications marked as rescue medications.

Concomitant non-drug therapies will be similarly listed by subject.

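### SAP 11.1 and 11.3 take epinephrine use from one CRF page, although 11.2 allows for records on other pages, so treated anaphylaxis could be tabulated as untreated

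*SAP*

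**What the plan says.** Four sections of the SAP bear on this.

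- **SAP 11.3 (Anaphylaxis Episodes)** repeats its summaries for two complementary sets. The first is "Episodes where epinephrine is administered on the same date (based on the Concomitant Medication CRF pages"). The second is "Episodes where epinephrine is not administered on the same date". The source page is named outright.
- **SAP 11.1 (Epinephrine Use as Rescue Medication)** names no page. It says: "Epinephrine use is defined as any rescue medication with a preferred name of 'EPINEPHRINE' when coded as described in Section 10.2", and it also requires documentation that the drug was given on a specific date.
- **SAP 10.2 (Prior and Concomitant Medications and Therapies)** is the section 11.1 points to. Its coding statement is: "All medications recorded on the Concomitant Medications CRF page will be coded using the World Health Organization drug dictionary". It describes no coding for medications entered on any other page.
- **SAP 11.2 (Summary of Rescue Medications)** says: "Non-study medications used during the course of the study may be recorded on CRF pages other than the Concomitant Medications CRF page". It goes on: "Information about epinephrine and other rescue medications and their frequency of use, will be consolidated and summarized" for the study report. On the table itself it says: "A table shell will be finalized prior to database lock but not included in the SAP".

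SAP 2.3.3 lists epinephrine use and anaphylactic episodes as exploratory safety endpoints.

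**The concern.** The SAP allows in 11.2 that the Concomitant Medications page may not hold every rescue drug, yet 11.3 names that page as its source and 11.1 leads back to it. The consolidation that could close the gap stands alone. Nothing in 11.1, 11.3, the table list in section 14.1.1 or the February 2015 addendum connects it to the epinephrine or anaphylaxis tables.

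Two outputs are exposed. SAP 11.1 says its aim is to count the subjects given epinephrine and the doses they received, and a single-page source could leave both counts short. In 11.3 an error would run in an unhelpful direction, since an episode that was treated would be reported as one that was not. If the 11.2 summary then showed a higher figure, the study report would hold two epinephrine counts with no rule saying which governs.

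**Working it through.** The documents state no count of epinephrine doses, no count of anaphylaxis episodes and no share of doses recorded off the Concomitant Medications page. There is therefore no plan figure to reproduce. The check is a comparison of sources, followed by arithmetic under a stated assumption.

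**1. Source of each output**

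| Output | Source as written | How it is fixed |
|---|---|---|
| 11.3, Tables 14.3.3.1 and 14.3.3.2 (epinephrine split) | Concomitant Medications page | Explicit |
| 11.1, Tables 14.3.8.3 and 14.3.8.4 | Concomitant Medications page | Inferred: 11.1 points to the coding in 10.2, and 10.2 codes that page |
| 11.2 consolidated summary | More than that page | Explicit, but its table shell is kept outside the SAP |

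The first two sources can be narrower than the third, and no sentence reconciles them.

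**2. Effect on 11.1.** Let m be the share of epinephrine administrations recorded only on other pages. This is an assumption, since the documents give no value. Then

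observed doses = true doses × (1 − m).

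For an illustrative 20 true administrations:

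- m = 0%: 20 × 1.00 = 20
- m = 10%: 20 × 0.90 = 18
- m = 25%: 20 × 0.75 = 15
- m = 50%: 20 × 0.50 = 10

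A subject drops out of the count only if every one of his or her doses in that category is missing from the page. Otherwise the subject stays but moves to a lower frequency row.

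Planned enrollment is about 50 subjects randomized 1:1, or about 25 per arm, so one missed subject is 1/25 = 4% of an arm. For the Exit food challenge, 11.1 uses as denominator only those who undergo it. Under the two scenarios in SAP section 4, 25 − 3 = 22 or 25 − 5 = 20 per arm would do so. One missed subject is then 1/22 = 4.5% or 1/20 = 5%.

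**3. Effect on 11.3.** Let T be the treated episodes, U the untreated ones, and k the treated episodes with no epinephrine on the Concomitant Medications page for that date. The table shows

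- epinephrine given: T − k
- epinephrine not given: U + k
- total: (T − k) + (U + k) = T + U.

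The first row is understated by the fraction k/T and the second is overstated by k episodes. The total does not change. The trigger summary and the overall count of subjects with an episode do not use the epinephrine source and are also unaffected.

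**4. Other controls in the SAP.** Site queries in 11.1 cover as-needed epinephrine prescriptions issued after dosing starts. They are not described as covering epinephrine given in clinic without such a prescription. Section 12 lists the items to be settled before lock, and reconciling epinephrine across CRF pages is not among them.

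**The case against.** A reader might infer that the epinephrine counts will be too low. The documents do not support that. SAP 11.2 says only that medications may appear on other pages, not that any dose appears there alone. A dose entered on both pages is not lost, and the CRFs are not available to settle the matter. Protocol 7.1 does not fill the gap: it assigns safety events and allergic symptoms to dedicated forms but does not say that treatment is recorded there instead of on the medication page. This part of the objection stands, and the point must stay conditional.

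A reader might also infer that a key safety result is at risk. SAP 2.3.3 ranks both endpoints as exploratory, no hypothesis test uses them, and total anaphylaxis counts are untouched. This also stands.

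The restriction in 11.1 can be read differently. The pointer to 10.2 may cite the drug dictionary and method rather than limit the source. It is fair to call the restriction an inference, though 10.2 sets out no route by which an entry on another page would be coded. In 11.3 there is no such ambiguity.

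Finally, the SAP has partial safeguards: the site queries, a monthly masked listing of epinephrine rescue medication (section 7.7), and use of the rescue-medication listings in quality control before the blinded review (section 12). The all-page summary in 11.2 is itself planned. These make a large loss less likely, but none supplies the missing link between 11.2 and the four tables.

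**Conclusion.** The point holds as an unreconciled source rule. SAP 11.3 explicitly, and 11.1 by cross-reference, rely on one CRF page, while 11.2 allows that relevant records may lie elsewhere and plans a consolidation that feeds neither.

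The consequence is conditional on at least one epinephrine dose being recorded only on another page. In that case the 11.1 tables undercount, the 11.3 tables move treated episodes into the row for episodes without epinephrine, and both can disagree with the 11.2 summary. The size is unknown and may be zero. Each affected subject is worth about 4% to 5% of an arm at the planned numbers. The effect is confined to exploratory, descriptive safety tables. A demonstrated undercount is not established.

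**What to change.** State in SAP 11.1 and 11.3 that epinephrine use is taken from the consolidated all-page data of 11.2, and make that the source for Tables 14.3.8.3, 14.3.8.4, 14.3.3.1 and 14.3.3.2. Three details need writing:

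- **De-duplication** by subject, date and time, so that a dose entered on two pages counts once. SAP 11.1 requires a documented date but not a time, so the rule must also say how two same-day records are handled when a time is missing.
- **Coding.** Extend the 10.2 coding to rescue medications entered on other pages, so that the preferred-name definition in 11.1 can reach them.
- **Shell.** Add the 11.2 table shell to the SAP, so that the consolidated count and the four tables can be seen to rest on the same data.

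The cost is small. The consolidation is already planned, so the added work is mainly the de-duplication rules, to be settled before database lock. If every dose is already on the Concomitant Medications page, no number changes.

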# **11.4 Imputation of MTD as Maximum CPNA Dose**

Subjects who do not undergo the Exit DBPCFC have the MTD for the Exit DBPCFC imputed as the MTD at the Screening DBPCFC, as described in Section 7.3. As an exploratory analysis, subjects randomized to CPNA who do not undergo the Exit DBPCFC will have their MTD for the Exit DBPCFC imputed as the higher of the Screening DBPCFC MTD or the highest tolerated dose of randomized study treatment tolerated during up-dosing. The highest tolerated dose is defined as the highest dose level taken for at least two weeks, which is not immediately followed by a dose reduction or withdrawal from the study.

The MTDs at the Exit DBPCFC will be summarized for the CPNA treatment group with and without this imputation scheme.

# **12 PRE-DATABASE LOCK DATA DETERMINATION**

The purpose of the pre-database lock blinded data review is the assignment of subjects to their appropriate study populations (ITT, mITT, PP), the classification of their responder status (Responder or Non-responder), and the designation of their response subcategory (for Responders - Passed Exit DBPCFC or *Ad libitum* peanut consumption; for Non-responders - Failed Exit DBPCFC, Reached 300 mg/day but Exit DBPCFC was not conducted, or Escalation Failure). The following items (listed below) will be finalized based on blinded data review, prior to database lock and unblinding. This blinded data review will be performed by study personnel who are blinded to all subject treatment assignments, as described in Section 7.7. The team involved in making these determinations and final index of listings reviewed by the team will be documented. Each of the items will be finalized and documented prior to database lock.

- Protocol violations, as described in Section 7.5, will be classified as major violations or minor violations.
- List of exclusions from analysis populations as described in Section 5. All subjects who were randomized but not included in 1 or more analysis populations (other than the Enrolled and Screening DBPCFC Only populations) will be reviewed.
- Responder status, as described in Section 6.10, will be reviewed and compared to disposition information (reasons for early discontinuation and reasons Exit DBPCFC not done), protocol violations, and adverse events to ensure correct classifications. Overall responder status, response subcategory, and reason for missing Exit DBPCFC, as described in Sections 6.9 and 6.10, will be finalized.
- Subjects who have added *ad libitum* peanut consumption to their diet and also had additional reasons for missing the Exit DBPCFC will have imputation rules for MTD of peanut determined on a case-by-case basis. If any subjects meet these criteria, the imputation rules and justification will be documented.
- Food allergy episodes will be reviewed and categorized as peanut-related or non-peanut related.

The listings displayed in Table 11.1 will be provided for the blinded data review, with randomized treatment group and subject identifiers masked as described in Section 6.13.

#### *Table 11.1*

Listing	Title
16.2.1.1	Subject Disposition
16.2.2	Protocol Deviations
16.2.3	Analysis Populations
16.2.5.1	Composite Dosing Information for Randomized Study Treatment
16.2.5.6	Screening and Exit Double-Blind Placebo-Controlled Food Challenge Results
16.2.5.7	Exit DBPCFC Maximum Tolerated Dose, Escalation Failure, and Responder Classification
16.2.7.9	Food Allergy Episodes

In those listings, the following variables will also be redacted (displayed as `XXX' or similar):

- Dates of randomization, first and last doses, last study visit, discontinuation/termination in disposition listing
- Dose dates and times in composite dosing information
- Dates and times in food challenge result listing.

The lead statistician, sponsor statistician, or blind data review personnel may request additional masked listings be prepared for the review.

Prior to conducting the blinded data review, the relevant data listings (above) will be thoroughly QC'd against related listings with subject numbers masked by a randomly created subject identifier, as described in Section 7.7. Related listings will include, at a minimum, listings pertaining to inclusion/exclusion protocol deviations (Listing 16.2.1.4), dosing (Listings 16.2.5.3, 16.2.5.4), AEs (Listings 16.2.7.1, 16.2.7.3, 16.2.7.4, 16.2.7.5, 16.2.7.6, 16.2.7.8, 16.2.7.9, 16.2.7.10) and rescue interventions (Listings 16.2.9.2, 16.2.9.3, 16.2.9.4, 16.2.9.5). The QC of the masked data listings will be conducted by the sponsor statistician, who will not otherwise participate in the blinded data review.

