#### 7.7 Maintenance of the Study Blind Prior to Database Lock

Due to the nature of the study, some data will be suggestive of randomized treatment assignment (specifically: allergy symptoms during dosing; Exit DBPCFC results; and adverse events, anaphylaxis episodes, concomitant medications and therapies, and IgG4 & IgE lab results after the first dose of randomized study treatment). The following procedures will be implemented to assist in maintaining the study blind among project team members during blinded data reviews prior to database lock (see also Section12):

- All tables and figures will be produced using surrogate randomization.
- All listings will have subject numbers masked by a randomly created subject identifier, which will be the same for each subject across listings. Listings may also include the surrogate randomized treatment used in the tables.

Although the study statistician and programming team does not have access to treatment assignments, they do have access to the actual subject identifiers and safety and efficacy data potentially suggestive of treatment assignment on a subject level basis. As a precaution, all advice by the lead statistician regarding study conduct issues will be documented. If a conflict arises, the lead study statistician will inform the project team, and if appropriate, the sponsor statistician and/or another statistician will be designated for this task. The study statistician

may attend decision-making meetings (see Section 12) to provide information as requested, but will not be involved in the decisions.

The sponsor statistician will not have access to the ARC002 treatment assignments (directly based on ARC001 treatment assignments) for subjects who roll over into ARC002. Similarly, the sponsor statistician will not have access to listings with actual subject identifiers or treatment information, and will not have access to the TEMPO database to view data directly. The sponsor statistician will receive subject listings, with surrogate and masked information as described above. The sponsor statistician will remain thusly blinded, in order to contribute to unbiased decisions made by the sponsor (see Section 12).

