Other sponsor representatives have access to subject tracking information, e.g., the dates of up-dosing visits, and will have access to ARC002 treatment assignments upon subject enrollment in that study, that, if combined, could be suggestive of treatment assignment on a subject level basis. These sponsor representatives may, however, still review blinded tables, with surrogate treatment information. Sponsor representatives involved in the pre-database lock blinded data review will only have access to a limited number of masked listings for conducting that blinded review (see Section 12). Additionally, the sponsor medical monitor and other sponsor representatives will have access to the masked listings described below in Table 7.3 for the purpose of ongoing safety review during the conduct of the study.

Output ID / Title	Frequency
LO1 Adverse Events	Monthly
LO2 Concomitant Medications: Epinephrine Rescue Medications	Monthly

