#### 9 EFFICACY ANALYSES

The ITT Population will be used for summaries and analyses of the efficacy parameters described below. The mITT and PP Populations will be used where indicated.

Screening and Exit DBPCFC food challenge results will be listed by subject and visit, with order (first or second) and date for both the peanut and placebo challenges, and time and presence of dose limiting symptoms listed for each individual dose administered.

The peanut MTD at Screening and Exit DBPCFCs, x-fold increase in peanut MTD, escalation failure status, desensitization response status and subcategory, and response subcategory for missed Exit DBPCFC will be listed by subject. DBPCFCs with indeterminate results, as defined in Section 9.2, will be flagged. Dose levels tolerated will be summarized by time point, dose level, food challenge (peanut or placebo), and randomized treatment group and overall.

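### The pre-lock review grades deviations and fixes mITT, PP and Completer exclusions with each subject's Exit challenge outcome in view: it is blinded to treatment label, but not to outcome

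*SAP*

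**What the plan says.** SAP Section 12 sets up a single pre-lock review with several tasks. Protocol violations "will be classified as major violations or minor violations". Exclusions from the analysis populations are settled. Responder status and subcategory are finalised. Imputation is decided case by case for ad libitum peanut consumers who had further reasons for missing the Exit challenge. The addendum (2.2) sends Completer exclusions to the same meeting.

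Table 11.1 lists what the team receives. Beside disposition, deviations, analysis populations, composite dosing and food allergy episodes, it includes:

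- Listing 16.2.5.6, "Screening and Exit Double-Blind Placebo-Controlled Food Challenge Results". SAP Section 9 describes the challenge listing as showing "time and presence of dose limiting symptoms listed for each individual dose administered".
- Listing 16.2.5.7, "Exit DBPCFC Maximum Tolerated Dose, Escalation Failure, and Responder Classification".

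The listings are supplied "with randomized treatment group and subject identifiers masked as described in Section 6.13". (Section 6 of the current SAP ends at 6.6; the masking text is in 7.7.) The further redactions under Table 11.1 are all dates or times, for example "Dates and times in food challenge result listing". SAP 7.7 keeps one masked identifier per subject across all listings.

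SAP 7.7 also states that "some data will be suggestive of randomized treatment assignment", and names Exit challenge results among those data. It adds that some sponsor representatives "will have access to ARC002 treatment assignments upon subject enrollment in that study".

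**The concern.** Because the masked identifier is constant, a reviewer can read a subject's deviation on one listing and that subject's Exit result on another. Nothing in Section 12 requires the deviation grade or the population decision to be fixed before the outcome listings are opened.

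The decision most exposed is Per Protocol membership. SAP 5.6 excludes subjects with major deviations that could affect the desensitization response. That is a judgement, and it should not be made with the response on the table. The mITT rule in SAP 5.5, which turns on whether a withdrawal was unrelated to treatment success or failure, also needs judgement, but it mostly concerns subjects with no Exit challenge.

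At stake is the value of the supportive analyses. SAP 9.2 relies on mITT and PP to show whether the primary result depends on imputing a response, and the Completer set is drawn from mITT. If exclusions can follow outcome, agreement between these analyses and the primary one is weaker evidence than it appears.

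**Working it through.** **1. The plan's own figures.** Inputs from SAP Section 4: about 50 subjects allocated 1:1 (25 per arm), two-sided 0.05, ITT rates of 58.7% versus 22% or 56.6% versus 20%, power at least 80%. The rates follow from the assumed dropout: 0.25 × 22/25 = 22%; 0.667 × 22/25 = 58.7%; 0.25 × 20/25 = 20%; 0.7075 × 20/25 = 56.6%. Summing the binomial probabilities of all significant tables under the SAP 9.1 rule (Pearson chi-square, or Fisher if an expected count is below 5) gives power of 80.0% and 80.2%. The plan's figures reproduce, and nothing below changes them.

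**2. Who has an Exit result to be seen?**

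| Decision | Exit result visible? | Analysis reached |
|---|---|---|
| Major/minor grading, PP membership | Yes, for anyone who was challenged | PP (supportive) |
| mITT exclusion of early withdrawals | Mostly no; non-responders by rule (SAP 7.3) | mITT and Completer (supportive) |
| Case-by-case ad libitum imputation | No; these subjects missed the challenge | ITT, if any occur |

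For the last two rows, Listing 16.2.5.7 still shows escalation failure and responder class.

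**3. How far does outcome reveal arm?** At 58.7% and 22% with equal arms:

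- P(CPNA given responder) = 0.587/(0.587 + 0.22) = 0.73, so P(placebo given responder) = 0.27.
- P(CPNA given non-responder) = 0.413/(0.413 + 0.78) = 0.35, so P(placebo given non-responder) = 0.65.

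Suppose one responder and one non-responder are excluded on outcome alone. The pair that favours CPNA (placebo responder, CPNA non-responder) arises with probability 0.27 × 0.35 ≈ 0.09. The opposite pair arises with probability 0.73 × 0.65 ≈ 0.48. Outcome knowledge alone therefore does not push towards CPNA; that needs a better guess at the arm.

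**4. How sensitive is a borderline result?** The counts and exclusions are assumptions, because the documents give none. With pooled proportion p, the statistic is X² = (p1 − p2)² / [p(1 − p)(1/n1 + 1/n2)].

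| Case | Counts | X² | p-value |
|---|---|---|---|
| No exclusions | 12/25 v 6/25 | 0.24²/(0.36 × 0.64 × 0.08) = 3.125 | 0.077 |
| One CPNA non-responder and one placebo responder out | 12/24 v 5/24 | 0.2917²/(0.3542 × 0.6458 × 0.0833) = 4.46 | 0.035 |
| One CPNA responder and one placebo non-responder out | 11/24 v 6/24 | 0.2083²/(0.3542 × 0.6458 × 0.0833) = 2.28 | 0.131 |

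All expected counts exceed 5, so the chi-square test applies in each row.

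**5. False-positive rate.** With a common 20% rate, 25 per arm and the SAP test rule, the exact chance of a significant result favouring CPNA is 2.2% with no exclusions. It is 5.6% if one CPNA non-responder and one placebo responder are always removed, and 12.3% if two of each are. If 1 to 5 non-responders are removed equally from both arms, it stays at 2.3% to 2.5%.

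**The case against.** The SAP promises a treatment-blind review and takes real steps to deliver one. Treatment and identifiers are masked and revealing dates are redacted. The team and its listings are documented, and every decision precedes lock. Finalising responder status is a stated purpose of the meeting, so outcomes must be seen at some point. Deviation categories (SAP 8.5) and a definition of a major deviation (Protocol 13.1) exist. The primary and key secondary tests use ITT. All of this stands and limits the severity. It does not explain why outcomes must be open while deviations are graded.

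Four stronger readings are tempting, and the documents do not support them.

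- A reader might infer that the primary result is open to the same bias. ITT membership needs no judgement, and ad libitum cases are largely governed by Table 7.1 and its note 4. SAP 7.3 regards such cases as unlikely.
- A reader might infer that mITT and PP are the only checks on imputation. The addendum adds the Completer set, and SAP 11.4 adds an exploratory re-imputation of the maximum tolerated dose.
- A reader might infer a bias towards CPNA. On outcome alone, the opposite pair of exclusions is the likelier one.
- A reader might infer that SAP 7.7 places holders of ARC002 assignments on the review team. It says those representatives may review blinded tables. It then describes representatives in the pre-lock review without saying whether they are the same people. Section 12 requires reviewers blinded to all assignments. The wording leaves the question open and shows no breach.

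**Conclusion.** The concern holds as a procedural weakness in the supportive analyses. Deviations are graded, and mITT, PP and Completer exclusions settled, by people who hold each subject's Exit outcome and can link it to that subject's deviations. The force falls mainly on major/minor grading and PP membership. It is slight for mITT, and it reaches the primary test only through a rare ad libitum classification.

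The documents allow no estimate of the bias, because neither the number of discretionary exclusions nor the reviewers' ability to guess the arm is known. The move from p = 0.077 to p = 0.035 is an assumed worst-direction case. It shows that at 25 per arm two exclusions can change a borderline supportive result, not that they would. The change is worth making because it is cheap and closes the route.

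**What to change.** Rewrite SAP Section 12 as a two-stage review.

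- **Stage 1.** Classify deviations, withdrawal reasons, ad libitum documentation and mITT, PP and Completer membership from the disposition, deviation and dosing listings. Withhold all Exit results and Listing 16.2.5.7, and strip responder-derived fields from the other listings. Apply the same limit to any extra listing the team requests. Sign off.
- **Stage 2.** Release the outcome listings to finalise responder status and subcategory. Stage 1 decisions stay fixed.

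State in SAP 7.7, consistent with Section 12, that no one with access to ARC002 treatment assignments may serve on the review team. While editing, correct the Section 12 cross-references to 6.9, 6.10, 6.13 and 7.5, which correspond to 7.3, 7.4, 7.7 and 8.5 in the current SAP.

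The cost is SAP wording, a second sign-off and a slightly longer pre-lock process. Sample size, power and the primary test do not change. Staging will not hide everything: disposition still shows who missed the Exit challenge, and dosing data may still hint at the arm. It does remove the Exit outcome from the decisions where judgement is greatest.
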